10.2. Populations for Analyses

For purposes of analysis, the following populations are defined:

Population	Description
Enrolled	All patients who sign informed consent
Randomized	All patients who are randomized at Week 0.
Modified Intent-to-Treat (mITT)	The mITT population is defined as all randomized patients who take at least one dose of study treatment. Patients will be included if they do not receive the correct treatment, or otherwise do not follow the protocol. Subjects will be analyzed according to the treatment to which they were randomized.
Safety	The safety population is defined as all randomized patients who receive at least 1 dose of study treatment and who did not discontinue from the study for the reason 'Lost to Follow-up' at the first postbaseline visit with no safety post-baseline data. Patients will be analyzed according to the treatment to which they were randomized.

Additional subpopulations may be identified. Full details will be provided in the study statistical analysis plan (SAP).

10.3. Statistical Analyses

10.3.1. General Statistical Considerations

Statistical analysis of this study will be the responsibility of Lilly or its designee.

Unless otherwise specified, the efficacy, health outcomes, and safety analyses will be conducted on the modified intent-to-treat (mITT) population.

All tests of treatment effects will be conducted at a 2-sided alpha level of 0.1, unless otherwise stated. No multiplicity adjustment will be used in this study.

Baseline will be defined as the last available value before the first dose of investigational product for both efficacy and safety analyses. In most cases, this will be the measure recorded at Week 0 (Visit 3). Change from baseline will be calculated as the visit value of interest minus the baseline value.

Any change to the data analysis methods described in the protocol will require an amendment ONLY if it changes a principal feature of the protocol. Any other change to the data analysis methods described in the protocol, and the justification for making the change, will be described in the clinical study report (CSR). Additional exploratory analyses of the data will be conducted as deemed appropriate.

10.3.1.1. Analysis Methods

The primary analysis for all continuous efficacy and health outcomes variables will use a mixed-effects models for repeated measures (MMRM) with treatment, [REDACTED]

[REDACTED] An unstructured covariance matrix will be used to model the within-patient variance-covariance errors. If the unstructured covariance matrix results in a lack of convergence, the heterogeneous Toeplitz covariance structure, followed by the heterogeneous autoregressive covariance structure will be used. The Kenward-Roger method will be used to estimate the denominator degrees of freedom. Type III sums of squares for the least-squares (LS) means will be used for all the statistical comparisons; the 90% confidence interval (CI) will also be reported. The LS mean difference, standard error, p-value, and CIs will also be reported. Treatment group comparisons at specific study visits will be tested using the t-test obtained from the MMRM results. Additional details of the MMRM method are described in Section 10.3.1.2.

The primary analysis for all categorical efficacy and health outcomes variables will use a logistic regression analysis with treatment, cohort, [REDACTED]

[REDACTED] The p-value and 90% (unless otherwise specified) CI for the odds ratio from the logistic regression model will be used for primary statistical inference. When logistic regression sample size requirements are not met, (<5 responders in any category for any factor), the p-value from the Cochran-Mantel-Haenszel (CMH) test with [REDACTED] [REDACTED] as factors will be used instead of the odds ratio and CI. Missing data imputation is described in Section 10.3.1.2.

10.3.1.2. Missing Data Imputation

As with any clinical study, patient dropouts and consequently missing data are expected. While every effort will be made to reduce missing data, the missing data imputation methods described below will be used to provide a conservative approach for assessing efficacy endpoints when patients have missing data.

The following imputation rules will be used:

- Last-observed-value-carried forward (LOCF): For analysis of categorical efficacy and health outcomes variables, LOCF will be used to assess a patient's response when data are missing at that endpoint. Randomized subjects without at least 1 postbaseline observation will be defined as non-responders for this analysis.
- Mixed-model repeated measures (MMRM): For continuous variables, the primary analysis will be a MMRM analysis with a missing-at-random assumption for handling missing data. This analysis takes into account both missingness of data and the correlation of the repeated measurements. No additional imputation methods will be applied to the MMRM analysis. Any observed data after permanent discontinuation of investigational product will be excluded from the MMRM analysis.

Full details of these analyses including missing data imputation methods and covariates will be provided in the SAP. Additional sensitivity analyses will be described in the SAP.

10.3.2. Treatment Group Comparability

10.3.2.1. Patient Disposition

All patients who discontinue from the study or the study treatment will be identified, along with their reason for discontinuation. Reasons for discontinuation from the study will be summarized by treatment group.

A detailed description of patient disposition will be provided at the end of the study.

10.3.2.2. Patient Characteristics

Demographic and baseline characteristics will be summarized descriptively by treatment group. Descriptive statistics including the number of patients, mean, standard deviation, median, minimum, and maximum will be provided for continuous measures, and frequency counts and percentages will be tabulated for categorical measures. No formal statistical comparisons will be made among treatment groups unless otherwise stated.

10.3.2.3. Concomitant Therapy

Concomitant medications will be descriptively summarized by treatment group in terms of frequencies and percentages using the safety population. The medications will be coded accordingly.

10.3.2.4. Treatment Compliance

Treatment compliance with the randomly assigned study medication will be evaluated at every clinic visit through the counts of returned investigational product tablets. A patient will be considered significantly noncompliant if he or she misses more than 20% (i.e., compliance <80%) of the prescribed doses during the study, unless the patient's investigational product is withheld by the investigator for safety reasons. Similarly, a patient will be considered significantly noncompliant if he or she is judged by the investigator to have intentionally or repeatedly taken more than the prescribed amount of medication.

10.3.3. Efficacy Analyses

10.3.3.1. Primary Analyses

The primary efficacy measure is the change from baseline in ALP at Week 12. An MMRM (as described in Section 10.3.1.1) will be used to test the treatment difference between baricitinib and placebo.

10.3.3.2. Secondary Analyses

Secondary efficacy and health outcomes variables will be assessed using the methods stated in Sections 10.3.1.1 and 10.3.1.2.

10.3.4. Safety Analyses

All safety data will be descriptively summarized by treatment groups and analyzed using the safety population.

Treatment-emergent adverse event (TEAEs) are defined as AEs that first occurred or worsened in severity after the first dose of study treatment. The number of TEAEs as well as the number and percentage of patients who experienced at least 1 TEAE will be summarized using the Medical Dictionary for Regulatory Activities for each system organ class (or a body system) and each preferred term by treatment group. SAEs and AEs that lead to discontinuation of investigational product will also be summarized by treatment group. Fisher's exact test will be used to perform comparisons between the baricitinib and placebo groups.

All clinical laboratory results will be descriptively summarized by treatment group. Individual results that are outside of normal reference ranges will be flagged in data listings. Quantitative clinical hematology, chemistry, and urinalysis variables obtained at the baseline to postbaseline visits will be summarized as changes from baseline by treatment group and analyzed using analysis of covariance (ANCOVA) with treatment and baseline value in the model. Categorical variables, including the incidence of abnormal values and incidence of AEs of special interest, will be summarized by frequency and percentage of patients in corresponding categories. Shift tables will be presented for selected measures.

Observed values and changes from baseline (predose or screening if missing) for vital signs and physical characteristics will be descriptively summarized by treatment group and time point. Change from baseline to postbaseline in vital signs and body weight will be analyzed using ANCOVA with treatment and baseline value in the model.

The incidence and average duration of investigational product interruptions will be summarized and compared descriptively among treatment groups. Further analyses may be performed and will be planned in the SAP.

10.3.5. Pharmacokinetic/Pharmacodynamic Analyses

All plasma baricitinib concentration-time data will be pooled and evaluated using population PK methods. A covariate screen of patient and study-specific factors will be included in the analyses based on factors investigated in previous and (if any) ongoing PK analyses, and on their relevance to the target population. Exploratory and/or model-based analyses, examining the

relationships between baricitinib exposure and efficacy and response endpoints will be conducted. Other analyses of efficacy and safety outcome measures may also be assessed as scientifically appropriate and warranted by available data. Details about the analyses to be conducted will be contained in the PK/PD analysis plan.

10.3.6. Other Analyses

Not Applicable.

10.3.6.1. Subgroup Analyses

Not Applicable.

10.3.7. Interim Analyses

A limited number of preidentified individuals may gain access to the limited unblinded data, as specified in the unblinding plan, prior to the final database lock, in order to initiate the final population PK/PD model development processes for final analyses. Information that may unblind the study during the analyses will not be reported to study sites or blinded study team until the study has been unblinded; this applies to Cohort A and Cohort B.

Data from patients in Cohort A will be summarized after all the patients have completed the study. These data will be available to Lilly and the DMC. No additional interim analyses are planned.

Unblinding details are specified in the unblinding plan section of the SAP or a separate unblinding plan document.

11. References

- [APA] American Psychiatric Association. (1994). Diagnostic and statistical manual of mental disorders (4th ed.). Arlington, VA, US: American Psychiatric Publishing, Inc.
- Dougados M, van der Heijde D, Chen YC, Greenwald M, Drescher E, Liu J, Beattie S, Witt S, de la Torre I, Gaich C, Rooney T, Schlichting D, de Bono S, Emery P. Baricitinib in patients with inadequate response or intolerance to conventional synthetic DMARDs: results from the RA-BUILD study. *Ann Rheum Dis*. 2017;76(1):88-95.
- [EASL] European Association for the Study of the Liver. EASL Clinical Practice Guidelines: The diagnosis and management of patients with primary biliary cholangitis. *Journal of Hepatology* 2017;67:145-72.

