5.1. Overall Design

Study I4V-MC-JAIV (JAIV) is a multicenter, randomized, double-blind, parallel, placebo-controlled, proof-of-concept Phase II study in patients with primary biliary cholangitis (PBC) who have an inadequate response or are intolerant to UDCA that will be conducted in 2 cohorts. Both cohorts will follow the same study schedule.

Cohort A

Cohort A is a randomized, double-blind, parallel, placebo-controlled cohort comprised of the first group of patients. At least twelve patients will be randomized to baricitinib 2-mg and at least eight patients will be randomized to placebo. Once Cohort A has fully enrolled, enrollment will be suspended.

Once all Cohort A patients have completed the 12 week treatment period their data will be reviewed by an external DMC.

The primary goal of Cohort A will be to assess the tolerability and safety of baricitinib 2-mg compared to placebo through Week 12. Efficacy measures, such as change in ALP will also be assessed to provide context for the benefit:risk ratio.

A DMC will oversee this study (Section 9.4.8.2).

Cohort B

Cohort B is a randomized, double-blind, parallel, placebo-controlled phase comprised of the second group of patients. At least twenty patients will be randomized to baricitinib 4-mg and at least twelve patients will be randomized to placebo.

Enrollment in Cohort B will begin only after the DMC review of Cohort A is complete and Lilly has received and accepted a recommendation to proceed.

Figure JAIV.1 illustrates the study design.

All procedures to be conducted during the study, including timing of all procedures, are indicated in the Schedule of Activities (Section 2). Section 7.6 describes permitted concomitant therapy. Study governance considerations are described in detail in Appendix 3.

Each cohort of the study consists of 3 periods:

Screening Period: The screening period is up to 49 days and begins when the patient signs the informed consent form (ICF). In exceptional circumstances, the screening window can be extended after consultation with the sponsor where local authorities permit. During the screening period, the investigator must confirm the patient meets all inclusion and no exclusion criteria for the study (Section 6). Two assessments of AST, ALT, ALP, and total bilirubin values are required prior to randomization (by at least two measurements obtained at least 4 weeks apart). If the AST, ALT, ALP, or bilirubin values from the second sample are increased more

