[figure not shown]
than 20% compared to the first sample (second test result/first test result >1.2) **and** the second sample exceeds the ULN, then the patient will be excluded (exclusion criterion 44). Screening procedures will be performed according to the Schedule of Activities (Section 2). Eligible patients will be randomized at Week 0 (Visit 3).

Treatment Period: At Visit 3 (Week 0, baseline) all assessments are completed and baseline laboratory samples obtained according to the Schedule of Activities prior to the first dose of investigational product for both cohorts. Randomized patients will take the first dose of investigational product at the clinic and pharmacokinetic (PK) samples will be drawn 15 minutes and 1 hour post dose.

Investigational product will be taken daily for 12 weeks. Clinical assessments and laboratory samples, including additional PK sampling, will be obtained at scheduled visits according to the Schedule of Activities (Section 2). Special timing considerations of administration of investigational product relative to PK sample collection at study visits are described in Section 9.5.

During the treatment period, in addition to randomized treatment, patients will also maintain their usual medication regimen for PBC (Section 7.6 for details on concomitant therapy).

Follow-up Period: Patients who complete the treatment period, as well as those who discontinue Study JAIV treatment early, will have a post-treatment follow-up visit (Visit 801) approximately 4 weeks after the last dose of investigational product.

Abbreviations: V = Visit; W = Week.

^a Patients able to tolerate ursodeoxycholic acid (UDCA) will take UDCA orally as background therapy during the study.

Figure JAIV.1.

Illustration of study design for Clinical Protocol I4V-MC-JAIV.

Patients in Cohort A and Cohort B will follow the same study schedule as outlined in this figure. Cohort A will randomize 12 patients to baricitinib 2-mg and 8 patients to placebo. After a DMC review of Cohort A data, Cohort B will then randomize 20 patients to baricitinib 4-mg and 12 patients to placebo.

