5.3. End of Study Definition

End of the study is the date of the last visit or last scheduled procedure shown in the Schedule of Activities (Section 2) for the last patient.

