9.4.8.2. Data Monitoring Committee

A DMC will oversee the conduct of this study. The DMC will consist of members external to Lilly. This DMC will be guided by the DMC charter. At a minimum the DMC will include the following who have previous DMC experience:

- a specialist with expertise in hepatology and
- a statistician.

The DMC will review and evaluate data from the 12 week treatment period from patients in Cohort A.

In addition, the DMC may be convened if 2 or more patients permanently discontinue due to safety. The DMC chair will determine if the full DMC needs to convene.

The DMC chair will have access to all SAEs as reported to regulatory authorities and may convene a meeting at any time.

Access to the unblinded interim data will be limited to the statisticians who conduct the interim analyses and the DMC. The statisticians conducting the interim analyses will be independent from the study team. The study team will not have access to the unblinded data.

Data that the DMC will review include, but are not limited to, reasons for study discontinuation, AEs including SAEs, clinical laboratory data and vital signs. The DMC may recommend continuation of the study as designed, temporary suspension of enrollment, or discontinuation of a particular dose regimen or discontinuation of the entire study. The DMC may request to review efficacy data to investigate the benefit/risk relationship in the context of safety

observations for ongoing patients in the study. Details of the DMC and interim safety analyses will be documented in a DMC charter.

In addition to the DMC members, a limited number of prespecified individuals may gain access to the unblinded PK, safety, and efficacy data (as specified in the unblinding plan) prior to the final database lock to initiate the exploration and/or final population of the PK/PD model development processes. Information that may unblind the study during the analyses will not be reported to study sites or the blinded study team until the database is locked.

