6.13. Safety Analyses

Analysis populations are defined in Section 6.1.1. Table JAIV.6.6 describes the analysis sets. “Analysis set” is a broad term used to define a set of definitions including the population, the treatment group(s), the time period(s), and the comparison(s) where applicable.

Table JAIV.6.6. Definition of Analysis Sets

Analysis Set	Analysis Population	Treatment Groups (Short Label)	Baseline Time Period	Postbaseline Time Period	Inferential Comparisons
Treatment (T)	Safety Population	Placebo, Bari 2 mg, Bari 4 mg	From screening to just before first study drug administration	From immediately after first dose of study drug to up to 30 days off drug follow-up time	When used: Bari 2 mg vs. placebo; Bari 4 mg vs. placebo
Treatment plus follow-up (T + FU)	Safety Population	Placebo, Bari 2 mg, Bari 4 mg	From screening to just before first study drug administration	From immediately after first dose of study drug to end of study participation.	When used: Bari 2 mg vs. placebo; Bari 4 mg vs. placebo

Abbreviation: Bari = baricitinib.

The planned safety analyses are consistent with compound-level safety standards, which are based on multiple sources, including company standards, internal and external subject matter experts, and cross-industry initiatives (e.g., white papers produced by a PhUSE Computational Science Working Group (a collaboration with FDA and PhUSE), published in the PhUSE Deliverables Catalog at <https://www.phuse.eu/white-papers>). Descriptions of the safety analyses are provided in this SAP; however, additional details (such as handling of unscheduled visits, missing data, etc.) are in compound-level safety standards.

The following statistical methods will be used for safety unless otherwise noted:

- The Fisher exact test will be used for treatment comparisons of proportions, and odds ratios with corresponding 95% confidence intervals will be presented where specified.
- Treatment differences in mean change for continuous measurements will be assessed using an analysis of covariance (ANCOVA) model fitting “baseline” as a covariate. Type 3 sums of squares will be used. In addition, the crude mean, standard deviation (SD), minimum, median, and maximum will be displayed.

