6.16. Interim Analyses and Data Monitoring

An interim analysis will be conducted under the auspices of a DMC according to the specifications set forth in the protocol.

A DMC will oversee the conduct of this trial. The DMC will consist of members external to Lilly. This DMC will follow the rules defined in the DMC charter, focusing on potential and identified risks for this molecule and for this class of compounds. The DMC will include at least 3 individuals including a chairperson independent of Lilly (external to Lilly) and independent of any third party organization (TPO) contracted by Lilly to conduct the study. The DMC will include at least 2 physicians (at least one specialist with expertise in hepatology) with experience as a DMC member, as well as a biostatistician with DMC and clinical trial experience.

The DMC will be authorized to review unblinded results of analyses by treatment group prior to database lock, including study discontinuation data, AEs including SAEs, clinical laboratory data, vital sign data, etc. The DMC may recommend to continue the study as designed; temporarily suspend enrollment, pending resolution of a specified issue; or discontinue the entire study. While the DMC may request to review efficacy data to investigate the benefit/risk relationship in the context of safety observations for ongoing patients in the study, no information regarding efficacy will be communicated. Moreover, the study will not be stopped for positive efficacy results nor will it be stopped for futility. Hence, no alpha is spent. Details of the DMC, including its operating characteristics, are documented in the Baricitinib Data Monitoring Committee Charter for Protocol I4V-MC-JAIV, and further details are given in the Interim Analysis Plan in Section 6.16.1.

Besides DMC members, a limited number of pre-identified individuals may gain access to the limited unblinded data, as specified in the unblinding plan, prior to the interim or final database lock, to initiate the final population PK/PD model development processes. Information that may unblind the study during the analyses will not be reported to study sites or blinded study team until the study has been unblinded.

Unblinding details are given in a separate blinding and unblinding plan document.

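### Does Protocol 10.3.7 set a later time point and a wider readership for the Cohort A summary than 5.1 and 9.4.8.2 allow?

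*Protocol*

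**What the plan says.** Three parts of the protocol describe the look at Cohort A.

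- Section 5.1 (Overall Design) gives the sequence: "Once all Cohort A patients have completed the 12 week treatment period their data will be reviewed by an external DMC". It also says "Once Cohort A has fully enrolled, enrollment will be suspended", and lets Cohort B start only once the DMC review is finished and Lilly has accepted a recommendation to go on.
- Section 9.4.8.2 (Data Monitoring Committee) gives the content: "The DMC will review and evaluate data from the 12 week treatment period from patients in Cohort A". It limits unblinded interim data to the DMC and the statisticians who run the interim analyses. Those statisticians are independent of the study team, which gets no access. A small prespecified group may also see unblinded data for PK/PD modelling.
- Section 10.3.7 (Interim Analyses) says "Data from patients in Cohort A will be summarized after all the patients have completed the study". It makes these data available to Lilly and the DMC and rules out any further interim analysis. It keeps unblinding information from sites and the blinded study team in both cohorts, and refers to the SAP or a separate document for the unblinding details.

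On follow-up, 5.1 says that patients, including early discontinuers, "will have a post-treatment follow-up visit (Visit 801) approximately 4 weeks after the last dose of investigational product". Section 5.3 adds "End of the study is the date of the last visit or last scheduled procedure shown in the Schedule of Activities". The SAP does not choose between the wordings; its section 6.16 says only "An interim analysis will be conducted under the auspices of a DMC according to the specifications set forth in the protocol".

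**The concern.** The protocol usually keeps treatment and study apart. Section 10.3.2.1 separates discontinuing one from discontinuing the other, and SAP 6.6 separates completing treatment visits from completing follow-up. On that usage, 10.3.7 waits for Visit 801 while 5.1 does not.

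Cohort A exists to assess safety and tolerability, and its review opens or closes the door to 4 mg, so the timing could matter. The SAP's treatment-period safety set (Table JAIV.6.6) runs "From immediately after first dose of study drug to up to 30 days off drug follow-up time". A review held the moment the last patient reaches Week 12 would leave that window unfinished for the last finishers. Waiting for Visit 801 would instead prolong the pause in enrollment.

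The recipient wording looks loose as well. Making the data available to Lilly, with no function named, sits awkwardly beside the access limit in 9.4.8.2. Cohort A supplies 8 of the 20 planned placebo patients in the primary comparison, so a leak of by-arm data to the study team would be unwelcome.

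**Working it through.** **1. What each section governs.**

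| Section | Governs | Event or content |
|---|---|---|
| Protocol 5.1 | when the DMC review follows | all Cohort A patients through 12 weeks of treatment |
| Protocol 9.4.8.2 | what the DMC reviews | data from the 12 weeks of treatment |
| Protocol 10.3.7 | when the data are summarized | all patients have completed the study |

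No row states a data cut-off. In 10.3.7, all the patients must mean all Cohort A patients, because a summary held until the whole trial ends could not serve the review that gates Cohort B.

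**2. Size of the possible gap.** Inputs from the Schedule of Activities: Week 12 is day 84 (±4), and Visit 801 is 28 (±4) days after the last dose.

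- Gap after last dose: 28 − 4 = 24 days to 28 + 4 = 32 days.
- Study day, taking the last dose at the Week 12 visit: 80 to 88 for Week 12, against 80 + 24 = 104 to 88 + 32 = 120 for Visit 801.
- Share of the time from first dose to Visit 801: 24/(84 + 24) = 22%; 28/(84 + 28) = 25%; 32/(84 + 32) = 28%.

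If 10.3.7 simply means the end of the 12 weeks, the gap is 0. The number of patients lacking Visit 801 at a Week 12 review depends on accrual, which the documents do not give, so no count is offered.

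**3. Which readings fit all three sections.**

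- *Loose reading.* Completing the study means completing 12 weeks. All three agree.
- *Not-before reading.* Section 5.1 sets the earliest moment for review, and the summary is made after Visit 801 but presents treatment-period data. All three agree again.
- *Two separate looks.* This does not fit, since 10.3.7 plans no further interim analysis.

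Under both readings that fit, the 12-week treatment period is complete for Cohort A before Cohort B opens. They differ only in whether the review waits for off-drug follow-up.

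**4. Recipients.** Appendix 1 defines an interim analysis as one of data split by treatment group, so it is hard to read 10.3.7 as giving Lilly only pooled data. Lilly is then best read as people outside the study team. That fits 7.3, which foresees a minimum number of Lilly staff seeing assignments and keeps the Lilly study team blinded. It also fits the restriction inside 10.3.7. Who they are is a matter for the unblinding plan, to which 10.3.7 and SAP 6.16 and 7 refer.

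**5. Effect on the plan's numbers.** The design figure is 81% power. With 20 per group, a difference of 65 U/L, SD 80 U/L and two-sided alpha 0.1, the noncentrality is 65/(80 × √(1/20 + 1/20)) = 2.57 on 38 degrees of freedom. The t-test power is 0.810, which matches. Neither the timing of the Cohort A summary nor its readership enters this calculation. SAP 6.16 states that the study will stop neither for positive efficacy nor for futility, so no alpha is spent under either reading.

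**The case for a change.** The best case for a change is that the protocol's own vocabulary favours the strict reading, that the SAP sends the reader back to the protocol without resolving it, and that a few words would cure it. On recipients, the Appendix 1 definition makes by-arm data the natural reading, so Lilly without a named function goes further than 9.4.8.2 does. The unblinding plan and DMC charter were not available here and cannot be assumed to settle either point.

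Some of this stands. The wordings do differ, and read alone the sentence on recipients is wider than the access limit.

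The consequence is missing, however. The argument about an unfinished safety window assumes that the DMC tables use the treatment-period safety set. SAP 6.16.1 does not say so and refers to the charter for detail. Nor does the DMC depend on the Cohort A package alone: under 9.4.8.2 its chair sees all SAEs reported to regulatory authorities and may call a meeting at any time. Which moment suits the review is a trade-off between fuller off-drug follow-up and a shorter pause in enrollment, and it is the sponsor's to make. On the blind, the explicit exclusion of the study team controls the general word Lilly.

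**Conclusion.** No change to the plan is needed. Section 10.3.7 uses a loose phrase for the Cohort A trigger and a general word for the recipient. The possible timing difference is nil, or 24 to 32 days after the last dose, and concerns off-drug follow-up only. Nothing in the primary analysis, power, alpha or stated blinding depends on it, and following the plan as written still gives a sound result.

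This rests on two assumptions: that Lilly in 10.3.7 means personnel outside the blinded study team, as 7.3 and 9.4.8.2 require, and that the unblinding plan and DMC charter are consistent with those sections. If the protocol were amended for other reasons, aligning the phrase with 5.1 and pointing to 9.4.8.2 would be tidy, but it would only write down what the other sections already imply.
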